5.3. Dose Modifications

The dose of the investigational drugs may be modified according to the toxic side effects of the investigational drugs. The options of dose modification include: dose interruption, dose reduction, change in route of administration, and discontinuation.

In this study, SHR-1210 treatment may be interrupted for up to 12 weeks;

In addition to treatment interruption, the dosage of SHR-1210 can be reduced to 3 mg/kg, q2w, for subjects with a body weight of less than 50 kg during the treatment.

Dose modifications caused by apatinib-related toxicity include: dose interruption, modification of method of administration (first modification: 5 days of drug administration followed by 2 days of dose interruption; re-modification: 7 day of drug administration followed by 7 day of dose interruption), and dose termination. A changed route of administration for apatinib shall never be resumed for the subject.

If apatinib-related AE occurs during the study, such as hypertension, proteinuria, or hand-and-foot syndrome, apatinib may be interrupted, and can be resumed, administered in a modified route, or discontinued accordingly when the toxicity resolves. Subjects may continue SHR-1210 as monotherapy if apatinib treatment is discontinued.

For immune-related toxicity occurring during the trial, such as immune-related pneumonia, hepatitis and colitis, the dosing of SHR-1210 and apatinib should be interrupted as appropriate. The dosing can be resumed when the toxicity returns to Grade ≤ 1 or baseline levels (for subjects with abnormal laboratory measurements such as ALT/AST and TBIL at baseline). The dosing of SHR-1210 should be resumed first. The dosing of apatinib can be resumed when no significant abnormality is observed within 7 to 14 days after SHR-1210 administration. The route of subsequent administration of apatinib should be modified.

During the study, in case of \geq Grade 3 immune-related pneumonia, \geq Grade 3 elevation in TBIL (recurrent), Grade 4 elevation in ALT/AST (recurrent), other Grade 4 immune-related toxicities (except for hypothyroidism), Grade 4 injection reactions, or the interruption of SHR-1210 administration for more than 12 weeks due to immune-related toxicity but the toxicity can still not return to \leq Grade 1 or baseline levels (subjects with baseline abnormality), the administration of SHR-1210 should be terminated permanently.

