	Normal baseline: Grade ≥ 3 Grade 1 at baseline: Grade 4	Yes	Yes	Toxicity returns to Grade ≤ 1	First onset: treat for 5 days and hold for 2 days; Second onset: treat for 7 days and hold for 7 days;	
TBIL elevation	Grade 2	Yes	Yes	Toxicity returns to Grade ≤ 1	First onset: Resume at original dose Second onset: treat for 5 days and hold for 2 days; Third onset: treat for 7 days and hold for 7 days;	1. Discontinue SHR-1210 treatment after > 12 weeks of interruption without return to Grade ≤ 1 ; 2. Discontinue SHR-1210 treatment if Grade ≥ 3 TBIL elevation recurs
	Grade ≥ 3	Yes	Yes	Toxicity returns to Grade ≤ 1	First onset: treat for 5 days and hold for 2 days; Second onset: treat for 7 days and hold for 7 days;	

Treatment-related toxicity		Grade	Whether to suspend		Criteria for resuming	Dose modifications for apatinib	Criteria for discontinuation
			SHR-1210	Apatinib			
	Other non-hematological toxicities	Grade 1	No	No	—	—	—
		Grade 2 (lasts for ≥ 7 d)	Yes	Yes	Toxicity returns to Grade ≤ 1	Resume at original dose	Discontinue SHR-1210 treatment after > 12 weeks of interruption without return to Grade ≤ 1 ;
		Grade 3	Yes	Yes	Toxicity returns to Grade ≤ 1	First onset: treat for 5 days and hold for 2 days; Second onset: treat for 7 days and hold for 7 days;	
SHR-1210-related toxicity	Capillary hemangioma	Grade 3	Yes	No	Toxicity returns to Grade ≤ 2	Resume at original dose	Discontinue SHR-1210 treatment after > 12 weeks of interruption without return to Grade ≤ 1 ;
Apatinib-related toxicities	Hypertension	Grade 3 (after corrective treatment)	No	Yes	Toxicity returns to Grade ≤ 1	First onset: Resume at original dose Second onset of Grade 3 hypertension: treat with apatinib for 5 days and hold for 2 days; Third onset of Grade 3 hypertension: treat with apatinib for 7 days and hold for 7 days;	Discontinue apatinib treatment if Grade 3 hypertension recurs after 2 modifications

Treatment-related toxicity	Grade	Whether to suspend		Criteria for resuming	Dose modifications for apatinib	Criteria for discontinuation
		SHR-1210	Apatinib			
	Hypertensive crisis	Yes	Yes	Toxicity returns to Grade ≤ 1	Permanently discontinue apatinib treatment	Discontinue apatinib treatment

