Proteinuria (without significant increase in blood creatinine)	Grade 3 (24 h protein urine quantification)	No	Yes	Toxicity returns to Grade ≤ 2	Treat with apatinib for 5 days and hold for 2 days; Second onset of Grade 3 proteinuria: treat with apatinib for 7 days and hold for 7 days;	Discontinue apatinib treatment if Grade 3 proteinuria recurs after 2 modifications
Hand-and-foot syndrome	Grade 3	No	Yes	Toxicity returns to Grade ≤ 1	Treat with apatinib for 5 days and hold for 2 days; Second onset of Grade 3 hand-and-foot syndrome: treat with apatinib for 7 days and hold for 7 days;	Discontinue apatinib treatment if Grade 3 hand-and-foot syndrome recurs after 2 modifications
Headache	Grade 2 headache lasting ≥ 7 d despite symptomatic treatment, or Grade 3 headache	No	Yes	Toxicity returns to Grade ≤ 1	Treat with apatinib for 5 days and hold for 2 days; Second onset: treat with apatinib for 7 days and hold for 7 days;	Discontinue apatinib treatment if the event recurs after 2 modifications

The investigator may consider suspend the treatment for subjects who experience persistent and significant toxicities despite symptomatic treatment, including persistent Grade 2 or higher non-hematologic toxicities (except for asymptomatic Grade 2 hypertension) lasting 2 weeks or longer, and abnormal laboratory findings (except $<2\text{g}/24\text{h}$ proteinuria). After the toxicity resolves, route of subsequent apatinib administration should be adjusted accordingly.

In the course of the study and based on the above regulations for dose modification, the investigator may modify the dose appropriately by comprehensively considering the drug-related toxicity in the subjects (if a subject experiences multiple Grade 2 drug-related toxicity and shows poor tolerance to the drugs, the route of apatinib administration can be adjusted after treatment interruption and toxicity recovery).

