During the trial, if a subject has fever ($>38\text{ }^{\circ}\text{C}$) and needs to use medications for corrective treatment, or in case of obvious wheezing, polypnoea, or symptoms of suffocation, the administration of SHR-1210 is skipped for the current or next scheduled time of SHR-1210 administration before the symptoms are recovered. After the symptoms are relieved and become stable for more than 7 days, the subjects are given SHR-1210 according to the subsequent dosing schedule. The possibility of pneumonia should be eliminated by imaging examinations before drug administration if necessary.

Once hypertensive crisis, cerebral hemorrhage, Grade \geq II pulmonary hemorrhage, other Grade \geq III hemorrhage, arterial thrombosis, or Grade IV venous thrombosis occurs during the trial, leukoencephalopathy syndrome, gastrointestinal perforation, the administration of apatinib should be discontinued, the administration of SHR-1210 should be interrupted and active symptomatic treatment should be given. The resumption of SHR-1210 treatment will depend on the toxicity recovery.

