In the clinical study of SHR-1210, the monitoring of signs and symptoms of immune-related hepatitis, such as liver discomfort and transaminase abnormal, in the subjects will be strengthened. A high-dose hormone therapy will be given to subjects with a Grade 2 and above event. For specific operations, refer to the followings:

Grade 2 event: 0.5-1 mg/kg/day of methylprednisolone or equivalent given via intravenous or oral administration. The changes in liver function indicators should be closely monitored. After the event recovers to Grade 1, the dose of hormone is slowly reduced in a period no less than 1 month.

Grade 3 event: 1-2 mg/kg/day of methylprednisolone or equivalent given via intravenous or oral administration. The changes in liver function indicators should be closely monitored. After the hepatitis recovers to Grade 1, the dose of hormone is slowly reduced in a period no less than 1 month.

If the hormone therapy does not improve or deteriorate the condition after 3-5 days, a combination therapy with immunosuppressants can be used for the treatment after discussion with the sponsor.

- **Immune-related enteritis**

In the clinical study of SHR-1210, the monitoring of signs and symptoms of immune-related enteritis, such as abdominal pain, diarrhea, and hematochezia, in the subjects will be strengthened. A high-dose hormone therapy will be given to subjects with a Grade 2 and above event. Subjects with a Grade 2 event can interrupt SHR-1210 and be treated, but subjects with a Grade 3 or 4 event should permanently discontinue SHR-1210.

- **Immune-related thyroid dysfunction**

Thyroid dysfunction can occur at any time during the study. Therefore, in the clinical study of SHR-1210, the thyroid functions of the subjects will be regularly examined to closely monitor the clinical symptoms of thyroid dysfunction. After the occurrence of immune-related hyperthyroidism, the subject should be given a high dose of cortisone/prednisone. Hormone replacement therapy is used for the treatment of hypothyroidism, but glucocorticoids are not applicable.

In the clinical study of SHR-1210, the monitoring of signs and symptoms of immune-related thyroid dysfunction in the subjects will be strengthened. A high-dose hormone therapy will be given to patients with Grade 3 or higher hyperthyroidism. Patients with Grade 4 event should permanently discontinue SHR-1210. Treatment discontinuation of SHR-1210 is not required for patients with Grade ≥ 2 hypothyroidism.

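### Protocol 5.3/Table 1 allows SHR-1210 to resume after several severe events for which Section 9 requires a permanent stop or withdrawal, and no sentence says which governs

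*Protocol*

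**What the plan says.** **Section 5.3, text.** For immune toxicity, "such as immune-related pneumonia, hepatitis and colitis, the dosing of SHR-1210 and apatinib should be interrupted as appropriate". It continues "The dosing can be resumed when the toxicity returns to Grade" 1 or below, or to baseline. The permanent-stop list that follows sets Grade 3 or above for immune pneumonia, has entries for recurrent liver abnormalities, and ends with "other Grade 4 immune-related toxicities (except for hypothyroidism), Grade 4 injection reactions" and failure to recover within 12 weeks.

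**Table 1.** Immune enteritis/colitis, residual immune events and infusion reactions have no rows of their own. The residual row, "Other non-hematological toxicities", suspends both drugs at Grade 3 and resumes at Grade 1 or below. SHR-1210 ends only after more than 12 weeks without recovery.

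**Section 5.3, end.** For a group of events that includes arterial thrombosis, Grade IV venous thrombosis and gastrointestinal perforation, "the administration of apatinib should be discontinued, the administration of SHR-1210 should be interrupted and active symptomatic treatment should be given". It then says "The resumption of SHR-1210 treatment will depend on the toxicity recovery".

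**Section 9.** The immune enteritis entry in 9.1 allows interruption at Grade 2, "but subjects with a Grade 3 or 4 event should permanently discontinue SHR-1210". The residual entry in 9.1 permanently ends study treatment at Grade 3 or 4. Table 4 in 9.2 permanently ends SHR-1210 for infusion reactions of Grade 3 or higher. Section 9.3 says that treatment is discontinued and the subject withdraws for arterial thrombosis, for a symptomatic venous thrombosis marked IV, and for gastrointestinal perforation.

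**The concern.** These are stopping rules for serious, sometimes life-threatening, toxicity, and two parts of the protocol body answer the same question differently. A site working from 5.3 could give SHR-1210 again, within the protocol as written, to a patient whom Section 9 says must not receive it. A site working from Section 9 would stop. A monitor would have no clear basis for calling either action a deviation.

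There is also a small reporting consequence. The incidence of adverse events leading to interruption or discontinuation (Protocol 2.2.2) would partly reflect which section each site followed.

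**Working it through.** The point is a comparison of texts. No design figure in the plan needs to be reproduced.

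**Step 1. SHR-1210 rules side by side**

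| Event | 5.3 / Table 1 | Section 9 | Result |
|---|---|---|---|
| (a) Grade 3 immune enteritis/colitis | Interrupt; may resume at Grade ≤1 | 9.1: permanent stop | Conflict |
| (b) Grade 3 immune event with no rule of its own in 5.3 or 9.1 | Permanent stop listed at Grade 4; Grade 3 row resumes at Grade ≤1 | 9.1: permanent stop of study treatment | Conflict |
| (c) Grade 3 infusion reaction | Permanent stop listed at Grade 4; nothing said on Grade 3 | Table 4: permanent stop | Thresholds differ; stopping at Grade 3 satisfies both |
| (d) Arterial thrombosis, gastrointestinal perforation | Interrupt; resumption allowed | 9.3: discontinue and withdraw | Conflict |
| (d) Venous thrombosis | Grade IV: interrupt; resumption allowed | 9.3: symptomatic, marked IV: discontinue and withdraw | Conflict if IV means Grade IV |

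Row (c) takes the injection reactions in 5.3 to be infusion reactions, since SHR-1210 is given only by infusion (5.1.5, 5.2).

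**Step 2. Rules that agree.** The two parts match for pneumonitis (stop from Grade 3), for nephritis, hypophysitis and hyperthyroidism (stop at Grade 4), for hypothyroidism (no stop) and for haemorrhage (resumption may be considered). Immune hepatitis has its own Table 1 rows and no stopping rule in 9.1. None of these is part of the point.

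**Step 3. Is there a precedence rule?**

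- Table 1 and 9.1 are both introduced as recommendations, and Table 4 as reference material.
- 5.3 gives its own rules a firmer label: "In the course of the study and based on the above regulations for dose modification, the investigator may modify the dose appropriately". It does not mention Section 9.
- 9.3 defers to the dose-modification principles for fatigue, but not for any event in the table above.
- Appendix 4 ends immunotherapy for Grade 3–4 diarrhoea/colitis but refers back to the protocol, and so back to the two rules.
- 4.3.1 ends treatment for unacceptable toxicity without defining it.

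None of these settles which text applies.

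**Step 4. How many patients?**

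- Planned size: 80 + 56 = 136, or 120 + 56 = 176 if the sorafenib-refractory group is expanded.
- Protocol 1.3.1 gives 214 subjects as 34.3% and 73 as 11.7%. Both imply 214/0.343 = 73/0.117 ≈ 624 subjects.
- It reports one diarrhoea SAE and no colitis SAE: 1/624 = 0.16% (Clopper-Pearson 95% CI 0.004% to 0.89%).
- Expected in this trial: 136 × 0.0016 = 0.2 (upper 136 × 0.0089 = 1.2), or 176 × 0.0016 = 0.3 (upper 176 × 0.0089 = 1.6). This is a rough guide to (a) only, because an SAE is not the same as Grade 3.
- The documents give no rate for all the groups together with apatinib 250 mg. At an assumed 1% to 5%: 136 × 0.01 = 1.4 to 176 × 0.05 = 8.8, or about 1 to 9 subjects.

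**The case against.** **The two texts can be followed together.** 5.3 is permissive, so a site that always uses the stricter rule breaks neither text. That is true, but nothing tells sites to do it.

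**The resumption sentence is general.** It also covers pneumonia, which the next paragraph stops from Grade 3, so event-specific stops limit it. This stands as a reading of that sentence. It does not remove the conflict: 5.3 sets no stop for colitis below Grade 4 apart from failure to recover, and the residual Grade 3 row in Table 1 allows resumption.

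**9.3 is about apatinib.** Its heading concerns apatinib-related reactions, and the perforation text speaks of one drug. But withdrawing from the trial ends SHR-1210 as well. For haemorrhage the same section says that resuming SHR-1210 may be considered; for thrombosis and perforation it does not.

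**The sponsor hears early.** Section 8.4 makes Grade ≥2 diarrhoea/colitis, Grade ≥3 infusion reactions and other Grade ≥3 immune events reportable within 24 hours, and 8.5 adds SAE reporting for Grade 3–4 infusion reactions. This makes unnoticed re-dosing less likely. It does not set a dosing rule.

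A reader might also infer three stronger things that the documents do not support:

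- *That 5.3 permits re-dosing after a Grade 3 infusion reaction.* Its list does not say that only Grade 4 counts, and applying the residual row of Table 1 to infusion reactions is an interpretation.
- *That venous thrombosis conflicts outright.* 9.3 omits the word grade and adds a symptom condition.
- *That time to treatment failure (SAP 4.1.2.9) is broadly distorted.* Under 5.3 apatinib may continue alone, so stopping SHR-1210 need not end treatment in (a) or (c). Any effect is confined mainly to (b), where 9.1 ends study treatment, and (d), where apatinib stops under both texts.

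**Conclusion.** The inconsistency is real and concerns patient safety. The rules conflict for Grade 3 immune enteritis/colitis, for Grade 3 immune events without their own rule, and for arterial thrombosis and gastrointestinal perforation. Venous thrombosis joins them if IV is read as Grade IV. Infusion reactions show a one-grade difference in the stated threshold, not a contradiction.

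The number affected is probably small. The range of 1 to 9 rests on an assumed rate, and the only rate in the documents bears on (a) alone. The case therefore rests on the seriousness of each event.

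It would be wrong to infer that the efficacy conclusion is at risk. The conflict does not alter the IRC-assessed response-rate test, and follow-up is kept after treatment ends (4.3.2, 6.3, 7.1.2).

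**What to change.** In the 5.3 permanent-stop list and in Table 1, give one SHR-1210 rule per event, using the stricter Section 9 rule by default:

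- permanent stop at Grade ≥3 for immune enteritis/colitis;
- permanent stop at Grade ≥3 for infusion reactions;
- permanent stop at Grade ≥3 for immune events that have no rule of their own;
- permanent stop after arterial thrombosis, Grade IV venous thrombosis or gastrointestinal perforation.

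Keep the existing event-specific rules explicitly: Grade 4 stop for nephritis, hypophysitis and hyperthyroidism, no stop for hypothyroidism, the hepatic rows and the capillary proliferation row. Without this, a general row for other immune events would pull the first three down to Grade 3, where 5.3 and 9.1 now agree on Grade 4.

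State whether the residual rule in 9.1, which ends study treatment, also stops apatinib, since 5.3 allows apatinib monotherapy. Write Grade IV in the venous thrombosis sentence of 9.3. Cross-refer Section 9 and Appendix 4 to the revised Table 1 and state that Table 1 governs.

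The cost is a protocol clarification and a letter to sites, with no new procedures or patients. The downside is that a few patients may stop SHR-1210 earlier than 5.3 would have required.

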	Normal baseline: Grade ≥ 3 Grade 1 at baseline: Grade 4	Yes	Yes	Toxicity returns to Grade ≤ 1	First onset: treat for 5 days and hold for 2 days; Second onset: treat for 7 days and hold for 7 days;	
TBIL elevation	Grade 2	Yes	Yes	Toxicity returns to Grade ≤ 1	First onset: Resume at original dose Second onset: treat for 5 days and hold for 2 days; Third onset: treat for 7 days and hold for 7 days;	1. Discontinue SHR-1210 treatment after > 12 weeks of interruption without return to Grade ≤ 1 ; 2. Discontinue SHR-1210 treatment if Grade ≥ 3 TBIL elevation recurs
	Grade ≥ 3	Yes	Yes	Toxicity returns to Grade ≤ 1	First onset: treat for 5 days and hold for 2 days; Second onset: treat for 7 days and hold for 7 days;	

Treatment-related toxicity		Grade	Whether to suspend		Criteria for resuming	Dose modifications for apatinib	Criteria for discontinuation
			SHR-1210	Apatinib			
	Other non-hematological toxicities	Grade 1	No	No	—	—	—
		Grade 2 (lasts for ≥ 7 d)	Yes	Yes	Toxicity returns to Grade ≤ 1	Resume at original dose	Discontinue SHR-1210 treatment after > 12 weeks of interruption without return to Grade ≤ 1 ;
		Grade 3	Yes	Yes	Toxicity returns to Grade ≤ 1	First onset: treat for 5 days and hold for 2 days; Second onset: treat for 7 days and hold for 7 days;	
SHR-1210-related toxicity	Capillary hemangioma	Grade 3	Yes	No	Toxicity returns to Grade ≤ 2	Resume at original dose	Discontinue SHR-1210 treatment after > 12 weeks of interruption without return to Grade ≤ 1 ;
Apatinib-related toxicities	Hypertension	Grade 3 (after corrective treatment)	No	Yes	Toxicity returns to Grade ≤ 1	First onset: Resume at original dose Second onset of Grade 3 hypertension: treat with apatinib for 5 days and hold for 2 days; Third onset of Grade 3 hypertension: treat with apatinib for 7 days and hold for 7 days;	Discontinue apatinib treatment if Grade 3 hypertension recurs after 2 modifications

Treatment-related toxicity	Grade	Whether to suspend		Criteria for resuming	Dose modifications for apatinib	Criteria for discontinuation
		SHR-1210	Apatinib			
	Hypertensive crisis	Yes	Yes	Toxicity returns to Grade ≤ 1	Permanently discontinue apatinib treatment	Discontinue apatinib treatment
Proteinuria (without significant increase in blood creatinine)	Grade 3 (24 h protein urine quantification)	No	Yes	Toxicity returns to Grade ≤ 2	Treat with apatinib for 5 days and hold for 2 days; Second onset of Grade 3 proteinuria: treat with apatinib for 7 days and hold for 7 days;	Discontinue apatinib treatment if Grade 3 proteinuria recurs after 2 modifications
Hand-and-foot syndrome	Grade 3	No	Yes	Toxicity returns to Grade ≤ 1	Treat with apatinib for 5 days and hold for 2 days; Second onset of Grade 3 hand-and-foot syndrome: treat with apatinib for 7 days and hold for 7 days;	Discontinue apatinib treatment if Grade 3 hand-and-foot syndrome recurs after 2 modifications
Headache	Grade 2 headache lasting ≥ 7 d despite symptomatic treatment, or Grade 3 headache	No	Yes	Toxicity returns to Grade ≤ 1	Treat with apatinib for 5 days and hold for 2 days; Second onset: treat with apatinib for 7 days and hold for 7 days;	Discontinue apatinib treatment if the event recurs after 2 modifications

The investigator may consider suspend the treatment for subjects who experience persistent and significant toxicities despite symptomatic treatment, including persistent Grade 2 or higher non-hematologic toxicities (except for asymptomatic Grade 2 hypertension) lasting 2 weeks or longer, and abnormal laboratory findings (except $<2\text{g}/24\text{h}$ proteinuria). After the toxicity resolves, route of subsequent apatinib administration should be adjusted accordingly.

In the course of the study and based on the above regulations for dose modification, the investigator may modify the dose appropriately by comprehensively considering the drug-related toxicity in the subjects (if a subject experiences multiple Grade 2 drug-related toxicity and shows poor tolerance to the drugs, the route of apatinib administration can be adjusted after treatment interruption and toxicity recovery).

During the trial, if a subject has fever ($>38\text{ }^{\circ}\text{C}$) and needs to use medications for corrective treatment, or in case of obvious wheezing, polypnoea, or symptoms of suffocation, the administration of SHR-1210 is skipped for the current or next scheduled time of SHR-1210 administration before the symptoms are recovered. After the symptoms are relieved and become stable for more than 7 days, the subjects are given SHR-1210 according to the subsequent dosing schedule. The possibility of pneumonia should be eliminated by imaging examinations before drug administration if necessary.

Once hypertensive crisis, cerebral hemorrhage, Grade \geq II pulmonary hemorrhage, other Grade \geq III hemorrhage, arterial thrombosis, or Grade IV venous thrombosis occurs during the trial, leukoencephalopathy syndrome, gastrointestinal perforation, the administration of apatinib should be discontinued, the administration of SHR-1210 should be interrupted and active symptomatic treatment should be given. The resumption of SHR-1210 treatment will depend on the toxicity recovery.

